Official Title: A combined workplace intervention including exercise and nutrition for health promotion in obese office workers: a randomized controlled study

NCT number (if available): It's not yet available.

Date of the document: 16/5/2026

1. Objective

Therefore, the main objective of this study is to design, implement, guide and evaluate the efficacy of a 6-month daily supervised workplace (during the working hours) combined intervention program including exercise (flexibility, balance, strength, aerobic capacity) and nutrition on selected health (body fat and circumferences, blood pressure, respiratory function, lipidemic profile), b) functional capacity indices (flexibility, static and dynamic balance, handgrip strength and aerobic capacity) and c) dietary habits (adherence to the Mediterranean diet, daily water consumption amount) of obese office workers. Another important objective of this study is to investigate the individualized responses per participant following the 6-month workplace intervention program. This is of fundamental importance since the individual characteristics of the participants may affect the efficiency of the intervention program and the generalization of study results in the whole population.

2. Methods

2.1. Participants

40 obese office workers (males and females), after announcements by the research team in four workplaces in the region of Western Thessaly in Greece, are expected to express interest in participating in the present study. The participants will be assessed for eligibility according to six inclusion criteria. In more detail, the participants: 1) should have at least 8 h per day in the office, 2) should have BMI value ≥ 30 kg/m², 3) should not have chronic diseases (physical or mental), 4) should not use any medication, 5) should not have injuries (in lower or upper body) the last 6 months and 6) should not participate in organized exercise programs or nutrition intervention during the last 6 months. Prior to the start of the study, the demographic, anthropometric, and working characteristics of the participants will be assessed using the American College of Sports Medicine (ACSM) health history questionnaire.

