2.4. Procedure

The present study will be conducted according to the Declaration of Helsinki and approved by the Ethics Committee of the University of Thessaly. Prior to the start of the study, the participants: (a) will be informed about the experimental procedures and possible risks, (b) will be familiarized with the testing and exercise procedures and (c) will be signed an informed consent form. Following the initial information and familiarization procedure, the baseline measurements will be performed inside the workplace setting (during the working hours) by the same investigators and under the same conditions. The sequence of measurements will be: (1) health indices, (2) functional capacity indices (a. flexibility, b. balance, c. strength and d. aerobic capacity) and (3) dietary habits questionnaire. Before the commencement of the functional capacity tests, the participants will be performed a standardized 8 min warm-up protocol (3 min chair-based aerobic dance, 5 min of static and dynamic stretching for lower and upper body). Following the baseline measurements, the participants will be randomly assigned in two equal groups: the IG and the CG. In the present study, a parallel

randomized controlled design will be used to investigate the efficiency of the 6-month workplace combined intervention program (exercise and nutrition) on health, functional capacity and dietary habits indices in obese office workers. Specifically, a computer-generated list of random numbers will be used for the allocation of the participants in one of the two groups (IG or CG). The main investigator will be blinded for the allocated intervention during the entire period of data collection, and the participants were requested not to discuss their intervention with the main investigator.

During the study, the IG will be participate in a daily 6-month (5 times per week) combined intervention program consisting of exercise and nutrition; while the CG did not perform any intervention during the 6 months. The exercise program of the intervention will be supervised by three exercise instructors of the research team, and special exercise attendance books will be filled in to confirm the participants' exercise adherence, while the nutrition part of the intervention will be supervised by the two nutritionists of the research team. After the end of the 6-month period, the baseline measurements will be repeated in the same order and at the same time of day.

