2.5. Statistical Analysis

All statistical analyses will be performed using the IBM SPSS Statistics v.31 software (IBM Corporation, Armonk, New York, NY, USA), and the results will be presented as means \pm standard deviations. Before the commencement of the study, a power analysis, using software package GPower 3.1, for statistical test "ANOVA: Repeated measures, within-between interaction (2 groups and 2 measures)" and effect size 0.30 (a err prob = 0.05) was performed. The statistical power analysis indicated that a total sample of 32 participants (16 participants in each group) would yield adequate power (0.90). The normality of the data will be examined using the Shapiro-Wilk test. Two-way analyses of variances (2-way ANOVAs) [2 groups (IG and CG) \times 2-time points (pre- and post-intervention)] with repeated measures on the "time-point" factor and Sidak pairwise comparisons will be applied to locate the significantly different means within and between groups. Independent t-tests will be also used to compare the percentage change (from pre- to post-measurement) between the two groups (IG and CG). The magnitude of the difference between measurements and groups will be examined using Cohen's *d* effect sizes (ES). The level of significance for all statistical analyses will be set at $p < 0.05$.

References

1. American College of Sports Medicine (ACSM) ACSM's Guidelines for Exercise Testing and Prescription. 9th ed. Lippincott Williams & Wilkins; Philadelphia, PA, USA: 2013. pp. 40–107.

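### Sex is in neither the allocation nor the model. A stable sex gap leaves the powered group-by-time test intact, but post-test group comparisons and Cohen's d lose precision and clarity.

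*Combined protocol and SAP*

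**What the plan says.** Section 2.1 plans for "40 obese office workers (males and females" and states no sex ratio or quota. It also collects demographic characteristics before the study starts.

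Section 2.4 places allocation after the baseline measurements: "the participants will be randomly assigned in two equal groups: the IG and the CG". The method is that "a computer-generated list of random numbers will be used for the allocation of the participants in one of the two groups". No stratification, blocking or minimisation is mentioned, by sex or by anything else.

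Section 2.5 bases the sample size on "ANOVA: Repeated measures, within-between interaction (2 groups and 2 measures", with effect size 0.30 and alpha 0.05, giving 32 participants for power 0.90. The analysis is a group-by-time repeated-measures ANOVA with Sidak pairwise comparisons to "locate the significantly different means within and between groups". It adds a second analysis: "Independent t-tests will be also used to compare the percentage change (from pre- to post-measurement) between the two groups (IG and CG". Cohen's d is to be given for differences between measurements and between groups. Sex is not a factor or covariate in any of these.

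**The concern.** Several outcomes listed in Section 1 (body fat, respiratory function, handgrip strength, aerobic capacity) may plausibly sit at different levels in men and women. If they do, pooling the sexes has two effects on any comparison of raw means at one time point. A chance difference in the sex mix of the arms moves the observed group difference, and the mixed-sex SD is larger than the within-sex SD, which widens the standard error and shrinks d.

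Section 2.5 plans such comparisons: the between-group Sidak contrast at post-test and a between-group d. Percentage change can also be touched, because the same absolute change is a smaller percentage for the sex with the higher baseline. At stake is how clearly these secondary readings of the data can be interpreted. Sex should be known from the entry questionnaire before anyone is allocated, so the plan could use it.

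**Working it through.** **Inputs.** From Section 2.5: N=32 (16 per arm), f=0.30, alpha 0.05, two groups, two measures. From Section 2.1: 40 expected volunteers, both sexes. Assumed, because the documents do not give them: pre-post correlation 0.5, half the sample men unless stated, a sex gap in level of 1–2.5 within-sex SD, and a sex gap in change of 0–1 SD. The within-sex SD is set to 1.

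**1. The plan's own figure.** For the within-between interaction, lambda = f² × N × m / (1 − rho) = 0.09 × 32 × 2 / 0.5 = 11.52, with 1 and 30 degrees of freedom. Power is 0.907 at N=32 and 0.887 at N=30, so 32 reproduces at correlation 0.5. The implied group difference in change is √(11.52 × 2 / 16) = 1.2 SD.

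**2. Chance imbalance.** With equal arms, the number of men in one arm is hypergeometric. The probability that the arms differ by 4 or more men is:

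| Randomised | Men | Probability |
|---|---|---|
| 32 | 8 | 22% |
| 32 | 12 | 27% |
| 32 | 16 | 29% |
| 40 | 10 | 27% |
| 40 | 20 | 34% |

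A difference of 4 men shifts the raw post-test difference by 4/16 × (1 to 2.5) = 0.25 to 0.63 SD at N=32, or 4/20 × (1 to 2.5) = 0.20 to 0.50 SD at N=40.

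**3. The powered test.** With two time points the interaction is a t-test on change, so a constant level gap subtracts out. In simulation (3,000 runs per setting, N=32) its standard error was 0.350, 0.351 and 0.354 SD for level gaps of 0, 1 and 2 SD, with power 0.90–0.92. If men and women also differ in change by 1 SD, power is 0.82–0.84 without sex in the model and about 0.90 with it.

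**4. The post-test contrast.** With half men, SE = √{(2/16) × [1 + (gap²/4) × 32/31]}:

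- gap 0: √0.125 = 0.35
- gap 1: √(0.125 × 1.258) = 0.40
- gap 1.5: √(0.125 × 1.581) = 0.44
- gap 2.5: √(0.125 × 2.613) = 0.57

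With sex balanced or adjusted for, it returns to about 0.35–0.36. For a true effect of 1.2 SD, the power of this contrast was 0.91, 0.82 and 0.63 at gaps of 0, 1 and 2 SD.

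**5. Cohen's d.** The mixed-sex SD is √(1 + gap²/4): 1.12, 1.25 and 1.60 at gaps of 1, 1.5 and 2.5. A d on the raw SD is smaller by those factors than one on the within-sex SD.

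**6. What sex adds to a baseline-adjusted model.** Pooling the sexes pulls the pre-post slope towards 1. At gap 2.5 and r=0.5 it is (0.5 + 1.5625) / (1 + 1.5625) = 0.80 instead of 0.50. Simulated standard errors at r=0.5:

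| Gap | Change score | Baseline only | Baseline + sex |
|---|---|---|---|
| 1.5 | 0.353 | 0.330 | 0.318 |
| 2.5 | 0.353 | 0.343 | 0.317 |

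For gaps of 1–2.5 SD, adding sex cuts variance by about 2–14% at within-sex r=0.5 (top end: 1 − (0.317/0.343)² ≈ 0.15 in one run, 1 − (0.321/0.346)² ≈ 0.14 in another). The cut is about 1–7% at r=0.7, where one run at gap 1 showed no gain (0.263 against 0.263). At r=0.9 there is none (0.159 against 0.159).

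**7. Cost in a plain change-score model.** If sex does not affect change and allocation is not balanced, adding sex raises variance by about 3–5%: (0.357/0.351)² = 1.03 at gap 1 and (0.362/0.354)² = 1.05 at gap 2.

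**The case against.** The strongest reply is that the trial is powered on the interaction, and a stable sex gap leaves that test alone. This stands. A reader might infer from the mixed-sex sample that noise and imbalance enter the main comparison; the planned test does not support that unless the sexes change by different amounts. The documents give no evidence on this. Section 1 says only that individual characteristics may influence the effect, without naming sex or promising a sex subgroup analysis.

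Other stronger readings also fail:

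- **A moderate imbalance is likely.** At 22–34% it is a minority outcome in every scenario examined.
- **The shift is as large as a real effect.** A shift of 0.25–0.63 SD is about a fifth to a half of the 1.2 SD implied by the sample-size calculation, and it needs both the imbalance and the assumed gap.
- **The test is biased.** Unstratified randomisation is valid; chance imbalance does not bias the test or raise the overall type I error.
- **Baseline adjustment is mostly wasted without sex.** This holds only near a gap of 2.5 SD, where about 30% of the variance gain is kept. At 1.5 SD about two thirds is kept. In any case the plan contains no baseline-adjusted model.

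It is also fair that the size of the sex gap is assumed, and that no case has been made for a large gap in every outcome, such as diet score or water intake. What survives is the exposure of the post-test contrast, the between-group d and possibly percentage change.

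**Conclusion.** The point holds in a limited form. Both sexes are enrolled, and sex is absent from the allocation and from every planned analysis. The powered interaction is not affected by a stable level gap. The post-test between-group comparison is: its standard error at N=32 rises from about 0.35 to 0.40–0.57 SD for an assumed gap of 1–2.5 within-sex SD with half the sample men. The between-group d shrinks if it is computed on the raw SD, and percentage change may be affected through its denominator.

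The loss is one of precision and interpretability, not validity. These sizes rest on sex gaps and a pre-post correlation that the documents do not supply. Severity: optional, low.

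**What to change.** 1. **Section 2.4:** balance the allocation list on sex, by stratified blocks or by minimisation if other factors are added, since strata would be small. This is one line in the allocation program and must be done before randomisation.
2. **Section 2.5:** make the between-group comparison of post values an ANCOVA with baseline and sex as covariates, so that between-group conclusions do not rest on unadjusted post-test means. Balancing alone is not enough: an unadjusted test would still estimate its error from the mixed-sex SD.
3. **Section 2.5:** if a between-group d is reported, give it also on the within-sex pooled baseline SD.

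The cost is a sentence or two in the analysis section and one residual degree of freedom. Where sex does not affect change, adding it to a plain change-score comparison brings no gain, and about 3–5% more variance if allocation is not balanced on sex. The interaction test can therefore stay without it. For outcomes with a within-sex pre-post correlation near 0.9, adding sex to the ANCOVA brings no benefit.

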2.2. Intervention

The IG will participate in a supervised 6-month combined intervention program (exercise and nutrition), which took place inside the workplace settings during working hours.

2.2.1. Exercise intervention

The IG will participate, every working day (5 days/week), in a 6-month supervised combined chair-based exercise program (120 training sessions; 25-40 min/day), including chair based seated and chair-assisted standing exercises to improve flexibility, balance, strength and aerobic capacity. The frequency of weekly exercise goals will be altered throughout the 6-month exercise intervention, according to the recommendations of the ACSM.

The exercise program will be implemented in small groups (4-5 participants per group), using a stable chair as the basic exercise equipment as well as portable auxiliary exercise equipment such as: a Pilates mini ball, a pair of silicone hand therapy balls, a pair of hand grippers and an exercise band for each participant. Each training session will be consisted of a 3-5 min warm-up, a 19-34 min main part of the program, and a 3-5 min cool-down. The training load gradually will be increased during the 6-month intervention program, according to the recommendation of the ACSM.

2.2.2. Nutrition and hydration intervention

The intervention regarding healthy diet and proper hydration will include 12 sessions (one session every two weeks) with the two nutritionists of the research team. It should be mentioned that for the implementation of the intervention will be used specifically designed educational material such as: a) presentations regarding the importance of healthy diet and proper hydration, b) educational leaflets with tips for healthy diet as well as indicative recipes for healthy snacks at the workplace, c) goal-setting cards for healthy options regarding nutrition and water consumption (Figure 2) and d) free application for proper hydration “Waterful” (<https://waterfulapp.com/?from=AppAgg.com>) where all the participants of the IG will be downloaded the to their mobile phone during the study.

2.3. Measurements

Before and after the completion of the 6-month workplace intervention program selected health and functional capacity indices will be assessed (Figure 1), using widely used, and reliable tests, that have showed high test-retest reliability (ICC = 0.95 - 0.98; SEM = 0.76 - 1.22; SEM% = 2.6 - 4) in office workers. Furthermore, the adherence to the Mediterranean diet was assessed before and after the 6-month time period using specific questionnaire.

[figure not shown]

Figure 1. Health, functional capacity and dietary habits measurements before and after the 6-month time period.

2.4. Procedure

The present study will be conducted according to the Declaration of Helsinki and approved by the Ethics Committee of the University of Thessaly. Prior to the start of the study, the participants: (a) will be informed about the experimental procedures and possible risks, (b) will be familiarized with the testing and exercise procedures and (c) will be signed an informed consent form. Following the initial information and familiarization procedure, the baseline measurements will be performed inside the workplace setting (during the working hours) by the same investigators and under the same conditions. The sequence of measurements will be: (1) health indices, (2) functional capacity indices (a. flexibility, b. balance, c. strength and d. aerobic capacity) and (3) dietary habits questionnaire. Before the commencement of the functional capacity tests, the participants will be performed a standardized 8 min warm-up protocol (3 min chair-based aerobic dance, 5 min of static and dynamic stretching for lower and upper body). Following the baseline measurements, the participants will be randomly assigned in two equal groups: the IG and the CG. In the present study, a parallel

randomized controlled design will be used to investigate the efficiency of the 6-month workplace combined intervention program (exercise and nutrition) on health, functional capacity and dietary habits indices in obese office workers. Specifically, a computer-generated list of random numbers will be used for the allocation of the participants in one of the two groups (IG or CG). The main investigator will be blinded for the allocated intervention during the entire period of data collection, and the participants were requested not to discuss their intervention with the main investigator.

During the study, the IG will be participate in a daily 6-month (5 times per week) combined intervention program consisting of exercise and nutrition; while the CG did not perform any intervention during the 6 months. The exercise program of the intervention will be supervised by three exercise instructors of the research team, and special exercise attendance books will be filled in to confirm the participants' exercise adherence, while the nutrition part of the intervention will be supervised by the two nutritionists of the research team. After the end of the 6-month period, the baseline measurements will be repeated in the same order and at the same time of day.

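### Allocation is not stratified by workplace and the analysis omits workplace; a half-split within each workplace plus a workplace term is a cheap improvement

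*Combined protocol and SAP*

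**What the plan says.** Section 2.1 expects "40 obese office workers (males and females") to come forward "after announcements by the research team in four workplaces in the region of Western Thessaly in Greece". It does not say how many are expected from each workplace, and the 40 are counted before eligibility screening.

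Section 2.4 states that "the participants will be randomly assigned in two equal groups: the IG and the CG". The only mechanism named is that "a computer-generated list of random numbers will be used for the allocation of the participants in one of the two groups (IG or CG"). No block size, stratum, fixed-size rule or half-split is given. On timing, "Following the baseline measurements, the participants will be randomly assigned", so the list of participants can be complete before anyone is allocated.

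Sections 2.2, 2.2.1 and 2.4 place the programme and the baseline measurements inside the workplace during working hours, with exercise in groups of 4-5. Section 2.5 plans a 2 (group) by 2 (time) repeated-measures ANOVA and t-tests on percentage change. Workplace enters neither. The power analysis in Section 2.5 gives 32 participants, 16 per arm, for power 0.90.

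**The concern.** Workplace organises recruitment, measurement and delivery, but plays no part in allocation or analysis. Two consequences follow.

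- **Precision.** If six-month change differs between workplaces for reasons unrelated to the intervention, an uneven split adds noise to the group comparison, and leaving workplace out of the model keeps that variation in the error term.
- **Delivery.** A workplace with 1-3, 6 or 7 intervention participants cannot form only groups of 4-5 from its own staff. The plan describes no training across workplaces.

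Both are settled at allocation. A workplace term can be added to the model later, but balance cannot be restored.

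**Working it through.** **Inputs from the documents:** four workplaces and 40 expected volunteers (2.1); equal arms (2.4); groups of 4-5 (2.2.1); f = 0.30, alpha = 0.05, N = 32, power 0.90 (2.5).

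**Assumptions not in the documents:** all 40 are randomised; 10 per workplace; pre-post correlation 0.5 and sphericity epsilon 1; workplace share of the variance in change of 5%, 10% or 20%.

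**1. The plan's own sample size.** For the within-between interaction, lambda = f² × N × m / (1 − rho), with m = 2, df1 = 1 and df2 = N − 2. At N = 32, lambda = 0.09 × 32 × 2 / 0.5 = 11.52 on 1 and 30 df, and power is 0.907. At N = 30 it is 0.887. So 32 is the smallest even total reaching 0.90, and the stated figure is reproduced at rho = 0.5.

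**2. Balance within workplace, taking the reading most favourable to the plan (20:20 forced).** The number of possible allocations is C(40,20) = 137,846,528,820. The probability of intervention counts a, b, c, d in the four workplaces is C(10,a) C(10,b) C(10,c) C(10,d) / C(40,20), with a + b + c + d = 20.

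- All four at 5:5: 252⁴ / C(40,20) = 4,032,758,016 / 137,846,528,820 = 2.9%.
- No workplace worse than 6:4, so every count is 4, 5 or 6:
  - 5,5,5,5: 4,032,758,016
  - one 4, one 6, two 5s: 12 × 210² × 252² = 33,606,316,800
  - two 4s, two 6s: 6 × 210⁴ = 11,668,860,000
  - total 49,307,934,816, or 35.8%.
- At least one workplace at 7:3 or worse: 1 − 0.358 = 64.2%.
- At least one workplace at 8:2 or worse, by the same enumeration: 21.1%.

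**3. Fit to groups of 4-5.** With 10 per workplace and 20 in the intervention arm, and each workplace contributing participants, all four can form only groups of 4-5 when the counts are 5,5,5,5 or 4,4,4,8. That is (252⁴ + 4 × 210³ × 45) / C(40,20) = 4.1%. A half-split within each workplace gives 5 every time. This depends on workplace size: with 16, 12, 8 and 4 participants, a perfect half-split gives 8, 6, 4 and 2, and the 6 and the 2 still do not fit.

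**4. Precision.** If workplace explains a share v of the variance in change and is balanced and modelled, the standard error falls by 1 − √(1 − v):

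| v | SE reduction |
|---|---|
| 5% | 2.5% |
| 10% | 5.1% |
| 20% | 10.6% |

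**5. Cost of the model term.** Four workplaces use 3 extra df. With no gain in variance, power goes from 0.907 to 0.905 at N = 32 and from 0.959 to 0.958 at N = 40. The required N stays 32.

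**6. Error rate.** In simulation (4,000 runs per setting, 10 per workplace, workplace share 0 to 20%), type I error without stratification was about 4-5%, with or without workplace in the model. With stratification but workplace left out, it fell to 3.8% (10% share) and 3.0% (20% share). Putting workplace in the model restored about 5%. Stratification and the model term therefore belong together.

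**The case against.** Four stronger readings are tempting, and the documents do not support them.

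- **That the list contradicts the promise of equal groups.** Coin-toss allocation of 40 people would give 20:20 only 12.5% of the time, since C(40,20) / 2⁴⁰ = 0.125. But the plan never says that the list is unrestricted. Allocation follows baseline, so ordering a known list of participants at random and cutting it in half fits the text, and gives equal arms for an even N. The method is unspecified; it is not shown to be inconsistent.
- **That chance imbalance biases the result.** It does not. Unstratified randomisation is valid, and the simulated error rate bears this out. Unequal arms also cost little: at 15:25, power is 0.947 (rho = 0.5).
- **That the planned ANOVA cannot deal with workplace differences.** With two time points, the group by time interaction tests within-person change, so stable workplace differences cancel. Only differences in change remain. The documents report no differences between the workplaces, and Section 2.4 has the same investigators measuring under the same conditions.
- **That any blocked scheme by workplace guarantees both kinds of balance.** Blocks of 4 with 10 per workplace give an exact 20:20 in only about 35% of runs, and the split can reach 16:24.

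Nor do the documents promise balance across workplaces. All of this stands, and it limits the point to a design improvement. It does not remove it: on the reading kindest to the plan, an uneven split in at least one workplace is still more likely than not under the assumed sizes.

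**Conclusion.** The point holds as a cheap improvement, not as a flaw in validity. The plan states no restriction for its random list, secures no balance within workplace and leaves workplace out of the analysis. With equal arms and an assumed 10 per workplace, there is about a 64% chance of a 7:3 or worse split somewhere and about a 3% chance of 5:5 everywhere. The benefit of acting is a standard error about 3%, 5% or 11% lower if workplace explains 5%, 10% or 20% of the variance in change, and intervention counts that suit groups of 4-5 better where workplace sizes allow. Workplace sizes and variance shares are assumptions. If workplace explains none of the variance in change, there is no gain in precision, and the loss is 3 df.

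**What to change.** In Section 2.4, state the restriction used. Once baseline measurements in a workplace are complete, allocate a random half of its participants to each arm. Where a workplace has an odd number, randomise the extra person so that the overall totals stay equal; this requires the odd workplaces to be handled together. Do not stratify further by sex: eight strata in about 40 people are too fine.

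In Section 2.5, add workplace by time to the repeated-measures ANOVA, or use workplace as a fixed effect in a model of change or a baseline-adjusted model. A workplace main effect alone in the repeated-measures ANOVA would leave the group by time test essentially unchanged.

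The cost is a slightly different randomisation script, one model term and 3 df (power about 0.907 to 0.905 at N = 32, assuming a pre-post correlation of 0.5). The allocation change has to be made before anyone is randomised.
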